9.1.2. SERIOUS ADVERSE EVENTS

A serious adverse event is one that at any dose (including overdose):

- Results in death
- Is life-threatening ¹
- Requires in-patient hospitalization or prolongation of existing hospitalization
- Results in persistent or significant disability or incapacity ²
- Is a congenital anomaly or birth defect
- Is an important medical event ³

¹ «Life-threatening» means that the subject was at immediate risk of death at the time of the serious adverse event; it does not refer to a serious adverse event that hypothetically might have caused death if it were more severe.

² «Persistent or significant disability or incapacity» means that there is a substantial

disruption of a person's ability to carry out normal life functions.

³ Medical and scientific judgment should be exercised in deciding whether expedited reporting is appropriate in situations where none of the outcomes listed above occurred. Important medical events that may not be immediately life-threatening or result in death or hospitalization but may jeopardize the subject or may require intervention to prevent one of the other outcomes listed in the definition above should also usually be considered serious. Examples of such events include allergic bronchospasm requiring intensive treatment in an emergency room or at home, blood dyscrasias or convulsions that do not result in in-patient hospitalization, or the development of drug dependency or drug abuse. A diagnosis of cancer during the course of a treatment should be considered as medically important. The List of Critical Terms (1998 adaptation of WHO Adverse Reaction Terminology Critical Terms List, provided in the «Instructions for completing the 'Serious Adverse Event/Expedited Report from a Clinical Trial' form») should be used as guidance for adverse events that may be considered serious because they are medically important.

Clarification of the difference in meaning between «severe» and «serious»:

The term «severe» is often used to describe the intensity (severity) of a specific event (as in mild, moderate, or severe myocardial infarction); the event itself, however, may be of relatively minor medical significance (such as severe headache). This is not the same as «serious», which is based on the outcome or action criteria usually associated with events that pose a threat to life or functioning. Seriousness (not severity) serves as a guide for defining regulatory reporting obligations.

9.1.3. DEFINITION OF ADVERSE EVENTS OF SPECIAL INTEREST (AESI)

An adverse event of special interest (AESI) is one of scientific and medical interest specific to understanding of the Investigational Product and may require close monitoring and rapid communication by the investigator to the sponsor. An AESI may be serious or non-serious. The rapid reporting of AESIs allows ongoing surveillance of these events in order to characterize and understand them in association with the use of this investigational product. AESIs for durvalumab include but are not limited to events with a potential inflammatory or immune-mediated mechanism and which may require more frequent monitoring and/or interventions such as steroids, immunosuppressant and/or hormone replacement therapy. These AESIs are being closely monitored in clinical studies with durvalumab monotherapy and combination therapy. An immune-related adverse event (irAE) is defined as an adverse event that is associated with drug exposure and is consistent with an immune-mediated mechanism of action and where there is no clear alternate aetiology. Serologic, immunologic, and histologic (biopsy) data, as appropriate,

should be used to support an irAE diagnosis. Appropriate efforts should be made to rule out neoplastic, infectious, metabolic, toxin, or other etiologic causes of the irAE. If the Investigator has any questions in regards to an adverse event (AE) being an irAE, the Investigator should promptly contact the Study Physician. AESIs observed with durvalumab include:

- Diarrhea/ Colitis and intestinal perforation
- Pneumonitis/ILD
- hepatitis / transaminase increase
- Neuropathy / neuromuscular toxicity (e.g. Guillain-Barré, and myasthenia gravis)
- Endocrinopathy (i.e. events of hypophysitis/hypopituitarism, adrenal insufficiency, and hyper- and hypothyroidism and type I diabetes mellitus)
- Rash/Dermatitis
- Nephritis/Blood creatinine increases
- Pancreatitis (or labs suggestive of pancreatitis - increased serum lipase , increased serum amylase)
- Myocarditis
- Myositis / Polymyositis
- Other inflammatory responses that are rare / less frequent with a potential immune-mediated aetiology include, but are not limited to, pericarditis, sarcoidosis, uveitis and other events involving the eye, skin, haematological and rheumatological events, vasculitis, non-infectious meningitis and non-infectious encephalitis

In addition, infusion-related reactions and hypersensitivity/anaphylactic reactions with a different underlying pharmacological aetiology are also considered AESIs.

Further information on these risks (e.g. presenting symptoms) can be found in the current version of the durvalumab Investigator Brochure.

9.1.4. RECORDING OF ADVERSE EVENTS AND SERIOUS ADVERSE EVENTS

Adverse events will be recorded CRF using a recognized medical term or diagnosis that accurately reflects the event. Adverse events will be assessed by the investigator for severity, relationship to the investigational product, possible etiologies, and whether the event meets criteria of an SAE and therefore requires immediate notification to AstraZeneca/MedImmune Patient Safety.

The following variables will be collected for each AE:

- AE (verbatim)

- The date <<and time>> when the AE started and stopped
- Changes in NCI CTCAE grade and the maximum CTC grade attained
- Whether the AE is serious or not
- Investigator causality rating against durvalumab (yes or no)
- Action taken with regard to durvalumab /comparator/combination agent
- Outcome

In addition, the following variables will be collected for SAEs as applicable:

- Date AE met criteria for serious AE
- Date Investigator became aware of serious AE
- AE is serious due to <<criteria>>
- Date of hospitalization
- Date of discharge
- Probable cause of death
- Date of death
- Autopsy performed
- Description of AE
- Causality assessment in relation to Study procedure(s)

9.2. DOCUMENTATION AND REPORTING OF ADVERSE EVENTS BY INVESTIGATOR

All adverse events that occur during the observation period set in this protocol must be documented on the pages provided in the case report form in accordance with the instructions for the completion of adverse event reports in clinical studies. These instructions are provided in the case report form itself.

The following approach will be taken for documentation:

- 1) **All adverse events** (whether serious or non-serious) must be documented on the «Adverse Event» page of the case report form.
- 2) If the adverse event is suspected, serious, and unexpected, the investigator must complete, in addition to the «Adverse Event» page in the case report form, a «Serious Adverse Event/Expedited Report from a Clinical Trial» form at the time the serious adverse event is detected. When this form is completed, designated staff member of the Korean Cancer Study Group should be notified by e-mail within 1 working day and it also should be reported to IRBs according to their procedures.
- 3) When a «significant overdose» of the investigational product occurs without an adverse event, the investigator should only complete a «Serious Adverse Event/Expedited Report from a Clinical Trial» form. Instructions on where to send this form will be provided by

the the Korean Cancer Study Group. In this case, there is no need to complete the «Adverse Event» page in the case report form.

- 4) Every attempt should be made to describe the adverse event in terms of a diagnosis. If a clear diagnosis has been made, individual signs and symptoms will not be recorded unless they represent atypical or extreme manifestations of the diagnosis, in which case they should be reported as separate events. If a clear diagnosis cannot be established, each sign or symptom should be recorded individually.

All subjects who have adverse events, whether considered associated with the use of the investigational products or not, must be monitored to determine the outcome. The clinical course of the adverse event will be followed up according to accepted standards of medical practice, even after the end of the period of observation, until a satisfactory explanation is found or the investigator considers it medically justifiable to terminate follow-up. Should the adverse event result in death, a full pathologist's report should be supplied, if possible.

All questions on the completion and supply of adverse event report forms and any further forms issued to the investigator at a later date to clarify unresolved issues should be addressed by the end of study.

REPORTING OF SAEs

All SAEs will be reported, whether or not considered causally related to the investigational product, or to the study procedure(s). The reporting period for SAEs is the period immediately following the time that written informed consent is obtained through 90 days after the last dose of durvalumab or until the initiation of alternative anticancer therapy. The investigator and/or Sponsor are responsible for informing the Ethics Committee and/or the Regulatory Authority of the SAE as per local requirements.

All SAEs should be reported to the Sponsor(PI): Send SAE report and accompanying cover page by way of email to AstraZeneca's designated mailbox:

[contact]

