8. STUDY PROCEDURE AND SCHEDULE

8.1. TABULATED OVERVIEW

Study Period	Screening	Study Treatment (-/+ 1 week)			Post Treatment (-/+ 2 weeks)
		Every cycle	Every 8 weeks	End of Treatment	Every 3 months
Study Procedures: Study Day:	D-14 to -1				
Informed consent	○				
Inclusion/Exclusion criteria review	○				
Demographics; medical history	○				
Complete physical examination	○	○		○	
Vital Signs	○	○		○	
ECOG performance status	○	○		○	
Electrocardiography ¹⁾	○			○	
Concomitant medication	○	○		○	
Chest X-ray	○		○	○	
Tumor Assessment (CT or MRI)	○		○	○	
Other imaging procedure if needed	○		○	○	
Assessment of response			○	○	
Toxicity assessment (CTCAE version 4.0)		○		○	
Survival					○
Subsequent treatment					○
CBC	○	○		○	
Chemistry ²⁾ , Amylase/Lipase	○	○		○	
CEA	○		○	○	
Thyroid function test (TSH, T3, free	○		○		

T4)					
Routine urinalysis	O				
Urine β -hCG pregnancy test ³⁾	O				
Height (screening only)/Weight	O	O		O	
Biomarker assessment ⁴⁾	O				

1) In patients without prior history of cardiovascular disease and showed normal electrocardiography, further examinations such as MUGA scan and echocardiography are not mandatory; however, patients with prior history of cardiac disease or those showed abnormal electrocardiography results, they would be checked with further examinations either with MUGA scan or echocardiography by the investigator's decision.

2) Chemistry labs include calcium, phosphorus, glucose, BUN, creatinine, total protein, albumin, AST/ALT, alkaline phosphatase, total bilirubin, uric acid and electrolytes(Na, K, Cl, Mg).

3) Urine β -hCG should be performed in women with child-bearing potential.

4) Perform tests for pertinent tumor markers if informative in the investigator's opinion and document at screening or as clinically indicated.

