8.5. POST-TREATMENT FOLLOW-UP (EVERY 3 MONTHS)

- Subsequent treatments (chemotherapy, immunotherapy or radiotherapy) and their responses
- Survival information on subject
- Status of disease and date of progression (in patients who stopped study treatment without documentation of disease progression)
- Date and cause of death

Telephone follow-up is acceptable. Site staff must use caution when contacting the subject's family for this information, especially if they are no longer under the care of the investigator, so as to not inadvertently cause any distress to the family of a subject who is no longer alive. Additional phone contacts will be required for formal survival sweeps at the time of primary analysis.

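### Serious events stay reportable for 90 days after the last dose, but no toxicity check is scheduled after End of Treatment and no collection period is set for other adverse events, so late immune-mediated events may be under-counted

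*Combined protocol and SAP*

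**What the plan says.** **Reporting window.** Section 9.2 requires that "All SAEs will be reported, whether or not considered causally related to the investigational product", from written consent "through 90 days after the last dose of durvalumab or until the initiation of alternative anticancer therapy". This rule names SAEs only.

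**Other AEs.** The same section says: "All adverse events that occur during the observation period set in this protocol must be documented". The AE definition in 9.1.1 also depends on a period of observation. Neither section gives its end, and no other section does. Section 9.1.3 says that AESIs may be serious or non-serious.

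**Scheduled checks.** In the table in 8.1, toxicity assessment is marked under the every-cycle and End of Treatment columns. The post-treatment column (every 3 months, with a window of 2 weeks either way) marks only survival and subsequent treatment.

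**Content of the later contact.** Section 8.5 lists "Subsequent treatments (chemotherapy, immunotherapy or radiotherapy) and their responses", "Survival information on subject", disease status with date of progression for those who stopped without it, and date and cause of death. It adds that "Telephone follow-up is acceptable". Section 7.9 and the synopsis list the same kinds of item. None has an adverse-event question.

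**Use of the data.** Safety and toxicity form a secondary objective (4.2). Section 10.3 bases the safety analysis on laboratory abnormalities and clinical AEs and gives no time window.

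**The concern.** A reporting window says what a site must pass on once it knows of an event. It does not create an occasion for the site to find out. Here the window runs for up to 90 days past the last dose, but the last planned occasion for asking about toxicity is End of Treatment. A patient who develops a new, non-fatal immune-mediated event after that enters the data only if the patient or another clinician tells the site.

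Non-serious events, including non-serious AESIs, are worse placed. With no end to the AE period, one site may record an event arising six weeks after the last dose and another may not, and both could claim to follow the protocol.

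At stake is the completeness of a descriptive secondary endpoint for an agent whose listed special-interest events are largely immune-mediated. The primary response endpoint, the sample size and the two-stage decision rule are not touched.

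**Working it through.** The plan states no figure on this point, so there is none to reproduce. The check is calendar arithmetic on the schedule.

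**Inputs from the documents**
- SAE window: 90 days after the last dose, or earlier if alternative anticancer therapy starts (9.2).
- First post-treatment contact: 3 months, give or take 14 days (8.1).
- Dosing interval: 4 weeks (7.2). Window for study-treatment visits: 1 week either way (8.1).
- Screening: day -14 to day -1 (8.1).

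**Assumptions, because the documents do not settle them**
- End of Treatment falls *t* days after the last dose, with *t* from 0 to 35. The upper value is one dosing interval plus the visit window: 28 + 7 = 35.
- The 3 months (taken as 91 days) run from End of Treatment.

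**Formulas**
- Days in the window with no scheduled toxicity check = 90 - *t*.
- First contact, in days after the last dose = *t* + 91 - 14 to *t* + 91 + 14.

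| *t* (days) | Days without a scheduled check | First contact (days after last dose) |
|---|---|---|
| 0 | 90 - 0 = 90 | 77 to 105 |
| 28 | 90 - 28 = 62 | 105 to 133 |
| 35 | 90 - 35 = 55 | 112 to 140 |

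So 55 to 90 days per patient have no scheduled check, and fewer if new anticancer therapy closes the window first. The contact may fall before day 90 (when *t* = 0) or wholly after it (when *t* = 28 or 35).

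**As a share of the patient's window.** Take *t* = 28, so 62 days are uncovered. After *k* cycles, the time from first dose to day 90 after the last dose is 28(*k* - 1) + 90 days. Up to 14 days of screening may be added, since the SAE window opens at consent.

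| Cycles | From first dose | With 14 days of screening |
|---|---|---|
| 2 | 62/118 = 53% | 62/132 = 47% |
| 4 | 62/174 = 36% | 62/188 = 33% |
| 6 | 62/230 = 27% | 62/244 = 25% |

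The uncovered time is 62 days in every row. Only the denominator changes.

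**Illustration of consequence (rates assumed, not in the documents).** Suppose all 33 planned patients are treated and a proportion *q* has a new event in the uncovered stretch, of which half are recorded. The chance that none is recorded is (1 - *q*/2)^33, against (1 - *q*)^33 with full capture.
- *q* = 5%: 33 × 0.05 = 1.65 events expected. The chance of recording none rises from 18% to 43%.
- *q* = 10%: 33 × 0.10 = 3.3 events expected. The chance rises from 3% to 18%.

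This shows only how sensitive a study of this size is to incomplete capture. It does not estimate the loss.

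**The case against.** The best case for the plan is that post-treatment events are not left uncovered. SAE reporting is mandatory whatever the cause. AEs already known must be followed to their outcome, even past the period of observation (9.2). Date and cause of death are collected every 3 months (8.5), so fatal events have a planned prompt. For patients who stop without progression, available tumour assessments are still recorded (7.9), so some contact may continue. The documents give no rate of immune-mediated events arising after stopping, so material under-counting is not shown. A telephone query would also rely on recall and would miss asymptomatic laboratory events, such as a raised lipase or creatinine.

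Much of this stands, and it limits the point. A reader might infer that late events depend on chance. The documents do not support that, because reporting is compulsory once a site knows. The exact description is passive capture of new-onset, non-fatal events. Following known events does not find new ones, and a cause-of-death field finds only fatal ones.

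A reader might also infer that patients who stop early contribute most of the uncovered time. They do not: for a given End of Treatment day, every patient who completes the window has the same uncovered time, and early stoppers merely have a larger share of a shorter window. Nor may the shares counted from first dose (53%, 36%, 27%) be read as shares of the whole SAE window, which opens at consent. They are the upper ends of ranges.

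**Conclusion.** The point holds in a limited form. The plan keeps SAEs reportable beyond the last scheduled toxicity check, and it refers to an AE observation period that it never sets. New-onset, non-fatal events after End of Treatment are therefore captured passively, and late immune-mediated events may be under-counted in the secondary safety objective.

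The size is up to 55 to 90 days per patient without a scheduled check. This rests on End of Treatment falling 0 to 35 days after the last dose, which the documents do not fix; a later visit would shorten the gap day for day, and new anticancer therapy would end it early. As a share of each patient's SAE window, with that visit 4 weeks after the last dose and no new therapy, it is about 47-53%, 33-36% and 25-27% for 2, 4 and 6 cycles. How many events would be missed cannot be derived from the documents. The change is worth making because it is cheap, not because the trial's main conclusion is at risk.

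**What to change.** 1. **Sections 8.1 and 8.5:** add an AE/SAE/AESI query with CTCAE grading to the first post-treatment contact. Anchor it to the last dose and make it at or shortly after day 90, by telephone if preferred. Ask about events up to day 90 or the start of new anticancer therapy, whichever comes first. Without this anchor, the existing 3-month window may fall before day 90 or well after it.
2. **Section 9.2:** state that the observation period for AEs and AESIs ends when the SAE window ends.
3. **Section 10.3:** tabulate events arising after the last dose separately from those on treatment.

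The cost is a few questions at a contact already planned and one case report form page. Reported toxicity may be slightly higher. The query relies on patient recall and will not detect asymptomatic laboratory events by telephone, which the report should state. For patients whose first contact has already passed, items 2 and 3 can still be applied to the data in hand.

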9.3. IMMEDIATE REPORTING BY INVESTIGATOR TO IRB AND MONITORING COMMITTEE

Serious, suspected, and unexpected adverse events and adverse events that fulfill a reason for expedited reporting to Pharmacovigilance must be documented on a «Serious Adverse Event/Expedited Report from a Clinical Trial» form in accordance with the «Instructions for completing the 'Serious Adverse Event/Expedited Report from a Clinical Trial» form. This form must be completed and supplied to the sponsor within 1 working day. The «Serious Adverse

Event/Expedited Report from a Clinical Trial» form and the instructions are provided in the investigator's study file.

The initial report must be as complete as possible, including details of the current illness and (serious) adverse event, and an assessment of the causal relationship between the event and the investigational product(s).

Information not available at the time of the initial report (e.g., an end date for the adverse event or laboratory values received after the report) must be documented on a follow-up «Serious Adverse Event/Expedited Report from a Clinical Trial» form.

The «Instructions for completing the 'Serious Adverse Event/Expedited Report from a Clinical Trial» form give more detailed guidance on the reporting of serious adverse events, adverse events that comply with alert terms, and adverse events initially reported as non-serious that become serious. In the latter situation, when a non-serious event becomes serious, details must be forwarded immediately to the Chief Principal Investigator on a «Serious Adverse Event/Expedited Report from a Clinical Trial» form.

9.4. OTHER EVENTS REQUIRING REPORTING

9.4.1. Timeline

If an event of medication error, drug abuse, or drug misuse occurs during the study, then the investigator or other site personnel informs the appropriate AstraZeneca/MedImmune representatives within 1 day, ie, immediately but no later than 24 hours of when they become aware of it. The designated AstraZeneca/MedImmune representative works with the investigator to ensure that all relevant information is completed within 1 (Initial Fatal/Life-threatening or follow-up Fatal/Life-threatening) or 5 (other serious initial and follow-up) calendar days if there is an SAE associated with the event of medication error, drug abuse, or drug misuse and within 30 days for all other events.

9.4.2. Medication Error

For the purposes of this clinical study a medication error is an unintended failure or mistake in the treatment process for study participants that either causes harm to the participant or has the potential to cause harm to the participant.

9.4.3. Drug Abuse

Drug abuse is the persistent or sporadic intentional, non-therapeutic excessive use of study intervention or AstraZeneca NIMP for a perceived reward or desired non-therapeutic effect.

9.4.4. Drug Misuse

Drug misuse is the intentional and inappropriate use (by a study participant) of study intervention for medicinal purposes outside of the authorised product information, or for unauthorised study intervention, outside the intended use as specified in the protocol and includes deliberate administration of the product by the wrong route.

